Site: University of Arkansas for Medical Sciences

adverse events are not expected as a result of this intervention, the PI will carefully monitor for any such event and report any adverse event to the IRB. In addition, if a peer has a relapse or any psychiatric emergency during the course of the intervention, they may contact [name] using the contact information provided during peer training. After this initial contact, [name] will debrief the peer by meeting with them and further discussing the situation.

Please note that although peers will receive mandatory confidentiality training required at the study institution, there is little concern that peers will “say the wrong thing” or break a patient’s confidentiality. Given that these peers have personal experience of hospitalization, it is more likely that they will be willing to guard the patient’s confidentiality and less likely than clinical staff to make insensitive remarks to a patient. However, all peers will be CITI-certified, with periodic reminders about patient confidentiality from the investigators.

Figure 1: Suicide safety planning training cycle

Description of interventions

Written safety plan: Please see separate upload for the Stanley et al version of the safety plan. This safety plan contains 6 components, and is completed by the patient themselves. This intervention takes approximately 20-40 minutes to complete. As a former site for the ED-SAFE study,¹² the UAMS ED typically has patients complete safety plans if being discharged. This is typically done by the psychiatric nurse or social worker if they are available, and this individual then places a progress note in the electronic medical record (EMR). These clinical providers must approve all safety plans in this study as peer support specialists and other research staff do not have the ability to place notes in the EMR.

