Stanley-Brown Safety Plan app (i.e., Safety Net app): The Safety Net app is an electronic version of a safety plan and it is available for download in Apple’s App Store. A preview of this app is available at: <https://apps.apple.com/us/app/stanley-brown-safety-plan/id695122998>. This app is owned by Two Penguins Studios, LLC. It was developed in partnership with the New York State Office of Mental Health. Unlike the paper version, the Safety Net app allows participants to email a copy of their safety plan to whomever they wish. It also allows patients to dial 911 or the National Suicide Prevention Lifeline from the app.

Please see Figure 2 below for study flow. The app only stores deidentified data locally on UAMS secured tablets. Thus, the safety plan will have to be shown or emailed to clinical staff in order to be entered into the electronic medical record. Please note that peers and other research staff do not have the ability to place notes in the EMR.

[figure not shown]

Figure 2. Study flow.

Study Design and Procedures

This is an effectiveness-implementation randomized controlled trial which will be conducted in the emergency department (ED) at the University of Arkansas for Medical Sciences (UAMS) in Little Rock, Arkansas. The UAMS ED is an urban emergency department which sees approximately 60,000 patients per year, including more than 1,200 suicidal patients.

This clinical trial will compare the intervention of ED patients completing an electronic safety plan with a peer or other research staff member to completing a traditional written safety plan with a peer or other research staff member. Patients triaged and flagged with the chief complaint of "SI", "suicidal ideation", "suicide attempt", or "Psychiatric BEE" on the ED trackboard when a peer or other research staff member is available will be approached to participate. Patients will be approached after evaluation by an emergency physician.

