Other measures: All participants will complete a brief questionnaire regarding their demographics, history of suicidal behaviors, and satisfaction with the safety planning process. After the visit, the electronic medical record will be searched for the following data: date/time of ED triage and disposition; length of ED stay; ED chief complaint or reason for visit; patient disposition (observation/admission/discharge/transfer); psychiatric diagnoses; and frequency of ED visits 3 months before and after the intervention. Length of ED stay will be compared against two control groups (obtained using AR-CDR): a) length of stay of all ED patients during a similar time period; and b) length of stay of ED patients who presented for SI during a similar time period. No PHI will be recorded for either of these deidentified control groups. Peers and other research staff will also be asked to record the total amount of time that they spent performing the safety plan intervention.

Study retention: The study duration is limited to the ED visit (typically <6 hours for SI patients), with participation in the study limited to the interventions mentioned above. Consequently, no special measures designed to increase retention are planned.

Title: Written safety planning vs the Safety Net app: A prospective randomized pilot trial
PI: [name], PhD
Site: University of Arkansas for Medical Sciences

Recruitment of peers for this project

Peers will be recruited through existing relationships with community suicide prevention organizations (i.e., Arkansas Foundation for Suicide Prevention, Arkansas Governor's Suicide Prevention Council, Veterans Service Organizations, etc.). Eligible recruits will complete an interview with [name] where they will be informed about the responsibilities and expectations of working with this project. Training and supervision of peers and other research staff will be used to further monitor the appropriateness of the individual to assist patients in providing the intervention.

Training of peers and other nonclinical individuals

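### Length of stay is compared with ED groups not selected as participants are; restrict the SI group, use the all-ED group as context, and report descriptively (low severity)

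*Combined protocol and SAP*

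**What the plan says.** The paragraph headed Other measures commits to an external comparison: "Length of ED stay will be compared against two control groups (obtained using AR-CDR): a) length of stay of all ED patients" in a similar period, and "b) length of stay of ED patients who presented for SI during a similar time period". It adds: "No PHI will be recorded for either of these deidentified control groups". No eligibility filter, hours of the day, disposition, matching or covariate is named for either group. The same paragraph provides a direct measure of workload: "Peers and other research staff will also be asked to record the total amount of time that they spent performing the safety plan intervention".

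Participants pass through more steps. Under Study Design and Procedures, patients flagged on the trackboard "when a peer or other research staff member is available will be approached to participate", and "Patients will be approached after evaluation by an emergency physician". The inclusion and exclusion criteria then require willingness to plan with non-clinical staff, no plan yet at this visit, age 18-89, English, and no custody, critical illness or intoxication, among others.

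The only length-of-stay figure in the document is under Study retention: "typically <6 hours for SI patients". Description of interventions says of the written plan: "This intervention takes approximately 20-40 minutes to complete". It also says that safety plans in usual care are typically completed for patients who are being discharged.

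**The concern.** Someone who sees participants' stays next to those of other ED patients will naturally ask whether study safety planning slows or speeds the visit. As defined, the comparison cannot answer that. Participants differ from both groups in who they are, when they came and how long they had already stayed when approached. Each of these can move length of stay without any effect of the intervention. A null result is equally hard to read, because selection could hide an effect as well as create one.

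The trial's other provisions do not fill the gap. Both randomised arms plan with study staff, so the randomised contrast speaks to app versus paper and not to study planning versus none. The adjustment rule in Data Analysis follows from comparing the randomised groups at baseline and is not stated to cover the external groups. Staff-recorded time is useful but is not length of stay.

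**Working it through.** The plan gives no effect size, standard deviation or sample size for length of stay, so there is no figure to reproduce. The check sets the selection rules side by side and then asks what selection alone could do.

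**1. Selection rules**

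| Condition | Participants | All-ED group | SI group |
|---|---|---|---|
| Similar time period | yes | yes | yes |
| Suicidal presentation | four trackboard flags, then SI or attempt | no | SI |
| Study staff available | required | not stated | not stated |
| Still in the ED after physician evaluation | required | not stated | not stated |
| Willing, no plan yet at this visit | required | not stated | not stated |
| Age, language, custody, critical illness, intoxication | restricted | not stated | not stated |

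**2. Composition of the all-ED group.** Study Design and Procedures gives about 60,000 patients a year, more than 1,200 of them suicidal. 1,200/60,000 = 0.02, so about 98% came for other reasons.

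**3. Selection in the SI group, with no true effect.** Let m be the mean stay of control visits that could have become participants, p the share of control visits that could not, and d the mean stay of the latter minus m.

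- Control mean = (1 - p)m + p(m + d) = m + p x d.
- Participants minus control = m - (m + p x d) = -p x d.

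The documents give neither p nor d, so these values are assumptions:

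- p = 10%, |d| = 0.5 h: 0.05 h = 3 minutes.
- p = 30%, |d| = 1 h: 0.3 h = 18 minutes.
- p = 40%, |d| = 2 h: 0.8 h = 48 minutes.
- p = 70%, |d| = 2 h: 1.4 h = 84 minutes.

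The nearest the documents come to p is the request to approach at most 100 patients to enrol 30, so up to 70/100 = 70% of those approached might not enrol. That is a ceiling requested for recruitment, not a forecast, and it leaves out patients never reached.

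**4. Direction.** The sign of -p x d is opposite to that of d. Requiring patients to be still present removes short stays and, taken alone, lengthens participants' mean. In an illustrative simulation with lognormal stays (assumed median 3-5 h, log-SD 0.4-0.6), requiring presence at 2 h raised the mean by about 2 to 43 minutes. The exclusions may work the other way if the excluded patients stay longer. The net sign is unknown.

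**5. Sampling error.** For 30 participants against a large control group whose mean is treated as known, the 95% half-width is 2.045 x SD/sqrt(30) = 0.37 SD. With an assumed SD of 1.5-3 h, that is about 34 to 67 minutes.

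**6. Overlap.** Participants are not stated to be removed from the SI group. At 1,200 suicidal patients a year, 30/1,200 = 2.5% over a year; over three months, 1,200/4 = 300 and 30/300 = 10%. Overlap shrinks a difference by that percentage, so it is minor.

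**The case against.** The strongest reply is that nothing rests on this comparison. Length of stay is listed among other measures. It is absent from the three research questions and from Outcomes 1-4, and no hypothesis, test or decision rule is attached to it. In a 30-patient pilot without a formal sample size calculation, much of any selection difference would lie within sampling error. This stands, and it keeps the severity low. It does not make the comparison informative as defined, and the remedy costs little if made before the extract.

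Three stronger readings are tempting, and the documents do not support them.

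- A reader might infer that the comparison is biased by a known amount or in a known direction. The minutes above come wholly from assumed p and d. The written plan's 20-40 minutes is no yardstick for a true effect either: it is the plan's duration, and usual care already includes plans for patients being discharged.
- A reader might infer that the SI group leaves out suicide attempts. The inclusion criteria do separate ideation from attempt, but Outcome 1 uses SI patients for everyone approached, and those patients carry all four flags. The wording is ambiguous and needs clarifying; it does not show an omission.
- A reader might infer that the protocol claims an effect on ED flow. It makes no such claim.

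A similar time period might also be meant to cover staffed hours. The text does not say so, and selection on eligibility, consent and continued presence would remain.

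**Conclusion.** The point holds as a low-severity, inexpensive improvement. As written, neither external comparison can separate selection from an effect of study safety planning. The all-ED group, about 98% non-suicidal, can give context only. The SI group is closer but lacks the eligibility, staffed-hours and still-present conditions that define participants. The size and direction of the resulting difference cannot be derived from the documents; the illustrations of 3 to 84 minutes rest on assumed shares and gaps. The main outcomes and the randomised contrast are not affected. How to handle the stays of withdrawn participants, and whether to report length of stay by arm, are separate matters.

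**What to change.** Before the AR-CDR extract is requested, add a short paragraph to Data Analysis that does the following.

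- Defines the SI group by the same four chief-complaint flags used for recruitment (SI, suicidal ideation, suicide attempt, Psychiatric BEE), stating that suicide attempt is included.
- Applies the eligibility criteria that AR-CDR can code: at least age 18-89, and language, custody, critical illness and intoxication where available.
- Defines the similar time period to include presence in the ED during staffed hours, where these are recorded. Presence matters here, not only arrival in those hours.
- Shows the comparison by disposition, which is already collected for participants and to which usual-care planning is tied. Disposition is settled after the intervention and the cells will be small, so this too is descriptive.
- Reports participants against the SI group as an estimate with a confidence interval, labelled descriptive, and gives the all-ED group as context with no test.
- States that the SI group may include clinician-completed plans and a small number of trial participants, and that selection on consent and on staying long enough to be approached remains.

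Because the control data are deidentified, these filters are best set before extraction. The cost is some query conditions, a record of staffed hours and a few sentences. The downside is a smaller SI group with some criteria only approximately coded. The documents do not describe the AR-CDR fields, so which criteria can be applied must be checked with the data holder.

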Specific training will be conducted about how to conduct the safety plan intervention, using materials developed by Brown & Stanley. Five learning objectives will guide the development of the training structure (please see Table I below). The instructor (Drs. [name] & [name]) will present information using various didactic and technological methods, and will take place over approximately 12 hours. During initial topics, the focus will be on building a safe learning environment that utilizes the peers' and other nonclinical individuals' personal life experiences to understand empirical evidence of suicide and suicide prevention. Later topics will provide more specific training on the safety plan using materials from Brown and Stanley.¹⁷ This portion of the training will also use videos, presentation slides, and role-playing. While lists of examples of warning signs, strategies for internal and external distractions, methods for restricting lethal means, and mental health treatment providers will be provided, peers and other nonclinical individual will be encouraged to provide input based on their own

Table I: Learning objectives in suicide safety planning training

Learning Objective	Learning Activities
1. Demonstrate active listening, genuineness, respect, and a desire to assist individuals at risk of suicide	
• Videos and Powerpoints about suicide and suicide prevention• Role play with instructor and other students
2. Demonstrate ability to develop a safety plan	
• Develop a personal suicide safety plan• Complete a safety plan using a written case study• Complete a safety plan as part of a role play activity• Verbalize plan to maintain appropriate self-care
3. Appropriately disclose personal experiences as a survivor suicidal ideations or attempts	
• Discuss beliefs of suicide and suicide prevention• Instructor will role model appropriate reflections of personal suicide experience• Practice appropriate self-disclosure
4. Demonstrate the ability to problem solve, risk assess, make suggestions for multi-professional referrals to maintain and ensure patient safety	
• Review referral and resource guide• Use case studies to practice how to appropriate refer for services and care
5. Demonstrate effective data collections and management	
• Review policies and procedures for data collections and management• Use case studies to practice data collection and management

experiences. Finally, training will also involve a general orientation to the emergency department. This part of the orientation will be provided by [name], and will involve already- developed training materials for orienting new research staff to the UAMS ED. Follow-up trainings will be provided depending on identified need.

Special training about COVID-19: all patients presenting to the UAMS ED are universally screened for COVID-19 signs or symptoms (fever, cough, recent travel) and are placed into specially-marked isolation rooms. As part of training, research staff must demonstrate awareness of ED policies regarding the marking of these isolation rooms for suspected COVID-19 patients; must understand the importance of not entering these rooms; must understand and agree to use hand sanitizers when entering and leaving a patient's room ("foam in/foam out"); must demonstrate awareness of UAMS policies regarding screening of employees when they arrive for work; and must agree to stay home if they are feeling sick.

Title: Written safety planning vs the Safety Net app: A prospective randomized pilot trial
PI: [name], PhD
Site: University of Arkansas for Medical Sciences

Please note that safety planning is a process that requires in-person interaction with participants due to the setting involved and confidentiality concerns. Having the special training detailed above in place reduces the health risk to potential participants and research staff. In addition to using the special training about COVID-19 detailed above, research staff will further minimize health risk by maintaining a safe social distance from participants during all study procedures and properly sanitizing all study equipment (pens, tablets, etc.) by using sanitizing wipes after use by each participant.

Supervision and debriefing of peers

Although anecdotally peers may be vulnerable to stress-induced relapse in the ED clinical environment, scant support for this idea is noted in the literature (please see above). Nonetheless, all peers will receive close supervision and debriefing during the study. Supervision will be provided using the discrimination model.¹⁸

As a licensed clinical counselor, [name] will assess the provider's skill level and will become the role of a teacher, counselor, or consultant based on need. In other words, peers and mental health staffs will be provided with either instruction and direct feedback (i.e., the teacher role), support for reflection and processing of personal experiences (i.e., the counselor role), or encouraging confidence in required skills (i.e., the counselor role) depending on need.

In terms of direct supervision, [name] will be on site during the first week of the intervention to observe performance and operation. She will ensure that the safety plan is being administered, documented, and managed appropriately by each provider (see also "Fidelity of the intervention" below). If deficits are identified, she will work with individuals to make needed improvements. During the first week of intervention implementation, [name] will also conduct an individual face-to-face interview with each peer. Interview questions will be guided by the Consolidated Framework for Implementation Research (CFIR)¹⁹ and focus on identifying and overcoming perceived barriers to implementation of the intervention.

Peers will also be provided with clear instructions on how to obtain help during any difficult or uncomfortable situations during the intervention. After the first week of the intervention, peers may inform ED clinical staff (social worker or psychiatric nurse) on site of such situations so that the staff may continue working on the safety plan with the participant. ED clinical staff are available 24/7 so peers would not have much trouble in finding and asking someone for help with a participant during these situations. Participants who do not complete the safety planning with a peer will be withdrawn from the study, but peers will be informed that their safety and well-being remains a priority when completing the intervention and so they should not hesitate to ask clinical staff for help. Peers may also contact [name] using the contact information provided during

Title: Written safety planning vs the Safety Net app: A prospective randomized pilot trial
PI: [name], PhD
Site: University of Arkansas for Medical Sciences

peer training in order to schedule an in-person meeting. [name] will debrief the peer at these meetings by further discussing the difficult or uncomfortable situations.

Once the pilot project is underway, periodic debriefing of providers will be provided by [name]. This debriefing will provide an opportunity to identify areas of needed improvement in the study protocol or in training (please also see “Fidelity of the intervention” below). Given this study utilizes individuals that have lived through serious suicide ideations and/or attempts, peers will likely have their own preconceived opinions about suicide and how to encourage survival. Debriefing will allow an opportunity to monitor how past experiences could be impacting the delivery of the intervention or how participating in the study could be impacting the provider. [name] will also use this time to review personal safety plans and encourage providers to participate in appropriate self-care.

Please note that training on other aspects of the proposed research has been provided by [name]. All research staff are trained on relevant IRB regulations & procedures, and required to be CITI-certified.

Measurement of safety plan quality: All safety plans will be evaluated by existing ED clinical staff for approval. If it needs to be modified, it will be documented that the research staff had to gather more information from the participant. Safety plans will also later be graded on a numerical rating scale (0-2 or 0-3, depending on grading component) by the investigators using materials developed by Gamarra et al for this purpose.²⁰ Using a “safety checklist,” responses for each of the 6 safety plan steps (with step 3 divided into two parts) and the “most important thing worth living for” section will be rated according to the personalization of the information in each section. In addition, each section will be independently rated for “completeness” (0=not complete, 1=partially complete, 2=complete) and “quality” (0=blank, 1=boilerplate, 2=some evidence of personalization, 3=highly personalized and specific). For instance, in the answer to the question “Warning signs (list 3 items),” patients may simply list “sad” which reflects a low-quality answer. Alternatively, the patient may answer “Feeling like I can’t stop crying or can’t stop being sad” which reflects a higher-quality more personalized answer. Each of the sections in a participant’s safety plan will be graded in this manner, with completeness having a maximum score of 16 and quality having a maximum score of 24. An overall score for the safety plan will be derived by adding the scores for all sections in a participant’s safety plan. Peers and other nonclinical individuals will be trained to coach participants towards higher-quality answers (please see above).

Monitoring: Adverse events or in case of psychiatric emergency

By definition, all patients have presented to the ED for an acute mental health crisis and will be under the care of trained ED physicians, trained ED nurses, trained

Title: Written safety planning vs the Safety Net app: A prospective randomized pilot trial

PI: [name], PhD

Site: University of Arkansas for Medical Sciences

psychiatric ED nurses who typically complete the safety plan, and other psychiatric personnel as appropriate. In the unlikely event of psychiatric decompensation, peers will be instructed to stop the intervention and seek help from qualified personnel in the ED. The intervention will then not be continued.

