Study flow: Utilizing trained nonclinical staff (i.e., peers or other research staff directed by the investigator team), staff will approach patients identified from the ED trackboard as being at risk for suicide until as many as 30 patients have been enrolled. Please see Figure 2 above for study flow. Patients are typically triaged by UAMS nursing staff as being "at-risk" after questions about self-harm. If so triaged, patients are then flagged with the chief complaint "SI", "suicidal ideation", "suicide attempt", or "Psychiatric BEE" on the ED trackboard and placed in a special area of the ED for evaluation. A partial waiver of HIPAA for recruitment purposes is requested to allow peers and other research staff to visualize the ED trackboard, and is appropriate for the following reasons:

- The PHI use or disclosure involves no more than minimal risk to the privacy of individuals based on the fact that no PHI will be recorded, reused, or

Title: Written safety planning vs the Safety Net app: A prospective randomized pilot trial

PI: [name], PhD

Site: University of Arkansas for Medical Sciences

disclosed to any other person or entity except as required by law or for authorized oversight of the research study.

- The research could not practicably be conducted without the requested waiver or alteration, as it would be difficult or impossible to identify ED patients at risk of self-harm in any other manner.
- The research could not practicably be conducted without access to and use of the PHI.

The trained peers and other research staff are UAMS nonclinical staff members who are participating in ED clinical research and who have received extensive training in safety planning (see below), data collection techniques, how to operate REDCap data collection software, and how to obtain informed consent. All are CITI certified and receive periodic reminders about confidentiality.

Upon approach by peers or other research staff, patients will be asked if they would like to participate in the study and if they would allow peers or other research staff to help them with safety planning. If the answer to both questions is yes, patients will be offered a brief screening procedure:

Inclusion criteria

- Presenting to the UAMS ED for suicidal ideation (SI) or after suicide attempt;
- Willingness to engage in safety planning with trained non-clinical staff;
- Have not already filled out a safety plan at the current visit

Exclusion criteria

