- Prospective participants <18-years or >89-years of age;
- Presently incarcerated or in police custody;
- Non-English speaking;
- Critically-ill;
- Intoxicated with alcohol or other substances;
- ED staff objected against entering room;
- Unwilling or unable to complete the safety plan electronically;
- Unwilling or unable to use a tablet;
- Unwilling or unable to show/email this safety plan to clinical and research staff.

Title: Written safety planning vs the Safety Net app: A prospective randomized pilot trial

PI: [name], PhD

Site: University of Arkansas for Medical Sciences

If participants indicate interest in the study and meet all inclusion/exclusion criteria, informed consent will be obtained using IRB-approved consent forms & processes. If they provide consent, participants (n=30) will be randomized in a 1:1 fashion to either the traditional written safety plan group, in which they will complete a written safety plan with a peer support specialist or other research staff member, or the electronic "Safety Net" safety plan group, in which they will complete an electronic safety plan with a peer support specialist or other research staff member (please see Figure 2 above).

Participants will be randomized using the randomization function in REDCap. All participants will be allowed to complete the safety plan in the privacy of their ED treatment room. Please note that participants will be given a \$25 gift card for participating regardless of which group they are randomized into for the study.

After completing the safety planning process, participants will then be asked to answer a short questionnaire concerning their demographics (e.g., age, biological sex), any history of previous suicidal ideation, suicide attempts, or related behaviors, and satisfaction with the safety planning process.

Regardless of whether the safety plan is completed in the traditional paper format or electronically, this will be shown to the UAMS ED psychiatric registered nurse or social worker for approval and entry into the EMR. Please note that the study will not otherwise modify care in the ED. It is possible, although not likely, that psychiatry consultants could choose to revise, edit, or otherwise start anew with safety planning for a particular patient. If so, the patient will be withdrawn from the study.

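### Investigators grade safety plan quality by judgement after the visit, and the plan neither masks them to arm nor fixes which version of each safety plan is graded

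*Combined protocol and SAP*

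**What the plan says.** Measurement of safety plan quality sets out the grading: "Safety plans will also later be graded on a numerical rating scale (0-2 or 0-3, depending on grading component) by the investigators". Each section receives a completeness rating ("0=not complete, 1=partially complete, 2=complete") and a quality rating that runs from 0 for a blank answer upwards ("1=boilerplate, 2=some evidence of personalization, 3=highly personalized and specific"). A worked example and a cited checklist support the ratings. Data Analysis, Outcome 3, places the grading after the patient's departure. The same section on quality has ED clinical staff approve every plan and allows a plan to be modified at that point.

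The trial is comparative: "This clinical trial will compare the intervention of ED patients completing an electronic safety plan" with a peer or other research staff member is set against completing a written plan with the same kind of help (Study Design and Procedures). The written arm produces a paper form. The app arm produces a plan on a research tablet: "Thus, the safety plan will have to be shown or emailed to clinical staff in order to be entered into the electronic medical record" (Description of interventions). Data Handling and Recordkeeping says that the app information is erased before each new patient and that safety plan material is kept in a locked file. The exclusion criteria imply that app plans also reach research staff, by being shown or emailed.

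None of these sections says that graders are masked to arm, or which version of a plan they grade.

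**The concern.** Separating some personalisation from high personalisation is a judgement. A grader who knows that a plan came from the app, or from paper, may make it differently without intending to. The people who grade are the investigators, who have an interest in how the two formats compare.

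At stake is the app-versus-paper difference in plan quality. A pilot of this size will estimate that difference imprecisely whatever is done, but imprecision does not excuse a bias that can be avoided. The version graded matters as well. If plans are graded after clinical staff have asked for changes, the score reflects that intervention as well as the format and the coaching.

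**Working it through.** **1. The scale.** The six steps, with step 3 split in two, give 7 sections, and the reasons-for-living section makes 8. Completeness: 8 × 2 = 16. Quality: 8 × 3 = 24. Both match the stated maxima. If the two are added, the total is 40 and the judgement-based quality part is 24/40 = 60% of it.

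**2. Which numbered outcomes can differ by arm.** Outcomes 1 and 2 (acceptance and eligibility) are settled at approach and screening. Under Study flow, "If the answer to both questions is yes, patients will be offered a brief screening procedure". Consent follows, and only then "participants (n=30) will be randomized in a 1:1 fashion". Of the four numbered outcomes, only 3 and 4 can therefore differ by arm. Outcome 4 is rated by the patient. Within Outcome 3, whether a plan has to be redone is decided in the ED. The graded score is the only part that the investigators rate by judgement.

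**3. How a grader could know the arm.** The original of a plan is either a paper form or app output. That these look different is an inference, but a strong one. Investigators also train the coaching staff (Training of peers and other nonclinical individuals), and a sub-investigator observes on site in the first week (Supervision and debriefing of peers). Either could reveal some allocations.

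**4. Whether any provision already masks the graders.**
- The statement that sections are rated independently concerns separate completeness and quality ratings. It does not describe masked or duplicate graders.
- The REDCap code and the nameless paper copy protect identity, not allocation.
- Clinical staff enter both kinds of plan in the medical record, which could supply a common text. But grading is not tied to that entry, the list of record data under Other measures omits it, and nothing says it is verbatim.
- The anchors, example and checklist narrow the judgement but do not hide the arm.

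**5. Source and version.** The retained plan is the likely source, given the locked file and the route by which app plans reach research staff. A patient whose plan is revised by psychiatry consultants is withdrawn, so the open question concerns plans modified at approval by the ED nurse or social worker. The section does not say which version of those is graded.

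**6. Size.** The documents give no SD, significance level or estimate of grading bias, so none can be derived. One illustration follows, resting entirely on assumed values. Take no true difference, 30/2 = 15 per arm, a two-sided 5% test on the quality score alone, and SD between 3 and 8 points. Suppose grading raises one section by one grade in every plan of one arm, a shift of 1 point. The noncentrality is (1/SD) × √(15/2), which is 0.91 at SD 3 and 0.34 at SD 8. With 28 degrees of freedom the chance of a significant result is then 14.3% and 6.3%, against 5% without the shift. Half a point gives 7.3% to 5.3%, and other assumed shifts give other rates.

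**The case against.** The strongest objection is that the comparison at risk is not specified. Outcome 4 refers to satisfaction with each method, whereas Outcome 3 speaks only of the quality of completed plans. The second research question asks whether plans are good enough for clinical personnel. Clinical approval and the count of redone plans address that question without using the investigators' grades. This stands in part: a reader might infer that Outcome 3 prespecifies an app-versus-paper test, and it does not. The comparison remains likely, because the trial is designed around the two formats and the analysis section plans adjustment for group differences and ANOVA for continuous variables.

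A reader might also infer that grading will certainly be unmasked. Silence does not show that. Figure 2, the plan form, the training agenda and the cited grading materials were not available to us. What can be said is that nothing in the protocol text requires masking. Nor should one conclude that the graders have no identifiable source, since the retained plan is the natural reading. The gap is the version.

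Finally, the illustrative rates should not be read as the trial's expected error. The shift, SD and significance level are all assumed. In a pilot without a formal sample size, possible bias in the estimated difference matters more than a false-positive rate.

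The objection that masking would be imperfect is fair. Content, illegible handwriting or an investigator's presence may still reveal the arm in some cases. That calls for recording those cases, and it does not justify leaving every plan unmasked.

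**Conclusion.** The point holds as an avoidable risk of assessment bias, of unknown size and direction, in a likely comparison of plan quality between arms. It is not an error in any stated figure, and the scale maxima are correct. It rests on three premises: that the graders work from plans whose format or history can reveal the arm, that the quality score will be compared between arms, and that no document outside the text we have already requires masking. The first two are well supported by the documents but not stated in them. The change is worth making because grading is done later and concerns wording, so masking can be added without touching the ED procedures. Confidence is medium.

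**What to change.** In Measurement of safety plan quality, state that grading is masked to arm and uses the same version in both arms, for example the plan as completed with research staff, before any modification at approval. Then:

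- Existing study staff who do not grade type each plan into one common REDCap form with the 8 section fields, under a new random ID, with no arm or format cue, and a second person checks the copy. App plans are captured before the tablet is erased for the next patient.
- Names and contact details are replaced by neutral role placeholders in both arms. Illegible or unclear words get one neutral marker in both arms.
- Plans are presented in shuffled order, and the investigators grade only from the form. Where possible, the grader is someone who did not observe the session.
- Any case in which the grader knew the arm is recorded and reported.

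**Cost.** No extra patients and no new assessor. Typing 30 plans at an assumed 15 minutes each takes 30 × 15 = 450 minutes, or 7.5 hours (5 to 10 hours at 10 to 20 minutes). Form set-up, copy checks and a protocol amendment come on top.

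**Downsides.** Layout cues are lost. Content, or an unclear-text marker that falls more often on handwriting, may sometimes reveal the arm. One more copy of sensitive text must be protected, in a study whose main stated risk is loss of confidentiality, so it needs the same access limits as the originals.
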